3.1 OVERALL OBJECTIVES

Our main objective is to evaluate the impact of an intervention consisting of default algorithm-based referrals, compared to usual practice, on outpatient palliative care visits and quality of end-of-life care among patients with advanced cancer. We hypothesize that this intervention will increase palliative care visits by 10 percentage points and decrease aggressive end-of-life utilization by 15 percentage points, relative to usual practice.

We will also explore physician and practice-related facilitators and barriers to completion via mixed-methods interviews. After completing initial enrollment, we aim to conduct a qualitative study through approximately 20 semi-structured interviews with:

1. medical oncology clinicians in the intervention group to understand the impact of the risk-algorithm and behavioral nudges on their workflow, and explore barriers and facilitators for feasibility, scalability, and ultimately increasing palliative care referrals for patients with advanced lung or non-colorectal gastrointestinal malignancies.
2. palliative care clinicians who saw patients referred through the study to explore their perspectives on seeing patients identified by the risk-algorithm and default referrals.

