4. STUDY DESIGN

4.1 RANDOMIZATION & RECRUITMENT

This 2-arm randomized trial (six-month enrollment; six-month follow-up) will enroll approximately 400 patients with advanced lung and gastrointestinal malignancies and 40 clinicians to assess response to behavioral nudges to refer to palliative care at up to 17 practices within Tennessee Oncology, a US community oncology network. All practices have access to palliative care and will be randomized to usual care vs. intervention. The outcome is completion of a palliative care visit within 3 months among high-risk patients.

We will randomize practices into two arms using permuted block randomization to balance practice size, baseline palliative care referral rate (see **Exhibit 1**). The Principal Investigator ([name]) and primary statistical analyst will be blinded to arm assignment.

This 2-arm randomized trial (six-month enrollment, six-month follow-up) is taking place at Tennessee Oncology. Tennessee Oncology, one of the nation’s largest, community-based cancer care specialists, is home to one of the leading clinical trial networks in the country.

Eligible clinicians will receive notification about the trial via email and in-person presentations. High-risk patients for the intervention will be identified from weekly runs of the risk score algorithm, in coordination with [name], Tennessee Oncology Care Data Systems Manager.

For the semi-structured interviews, the research team at Tennessee Oncology will create a list of potential clinicians. We will initially contact potential participants via email (see **Exhibit 6**), and if we do not get enough participation, coordinator and site investigator will do in-person recruitment with clinicians. For participants that agree to do the interview, clinical research coordinator will create a research ID for each participant that only key members of research team will have access to. Coordinator will subsequently create a de-identified dashboard to track mode of interview (in-person, virtual, telephone), length of interview, participant characteristics (gender, years in practice, palliative care v oncology, physician v nurse practitioner), and to store audio files, transcripts, and analysis documents. To ensure an adequate number of perspectives on the trial, we will use purposive

sampling to sample clinicians who performed at or above vs. below the median response to the intervention.

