4.3 STUDY DURATION

- 12 months (6 months enrollment; 6 months follow-up)
- We anticipate the semi-structured interviews take approximately three to four months. In a qualitative study, interviews are conducted until thematic saturation is achieved, and we anticipate this will be achieved with interviewing approximately 10 oncology clinicians in the intervention group and 10 palliative care clinicians.

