4.5 INCLUSIONS/EXCLUSIONS

Eligible clinicians will be medical oncology physicians and advance practice providers (APPs) practicing at Tennessee Oncology. Clinicians will be clustered to a single practice for the intervention and analysis in-order-to avoid contamination of intervention effect into the usual care arm. Patients will be excluded if they had a palliative care visit or had no medical oncology visit within the prior 12 months or are seen for a non-medical oncology encounter.

Eligible clinicians will receive notification about the trial via email and in-person presentations. High-risk patients for the intervention will be identified from weekly runs of the risk score algorithm (see **Exhibit 1**), in coordination with Tennessee Oncology Care Data Systems Manager.

Practicing medical oncology care clinicians that were in the intervention arm of our initial study and practicing palliative care clinicians at Tennessee Oncology are eligible for the semi-structured interviews. Medical oncology clinicians at Tennessee Oncology that were in control arm will be excluded.

Inclusion Criteria

- Clinicians:

- Medical oncology physicians and advance practice providers (APPs) practicing at Tennessee Oncology
- Patients:
 - Stage III and IV lung, and non-Colorectal GI cancers, defined using internal algorithms based on International Classification of Diseases (ICD) diagnosis codes, EHR entries, and manual screening
 - Received cancer treatment (chemotherapy or immunotherapy) in the past 6 months

Exclusion Criteria

- Patients:
 - Benign hematology, genetics, survivorship encounters; no prior EHR data;
 - Deceased or enrolled in hospice care
 - Had a palliative care visit within the prior three months
 - have not had a medical oncology visit within the prior 6 months or are seen for a non-medical oncology encounter

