4.7 INNOVATIONS

Prior retrospective studies have analyzed the effect of educational or trigger-based strategies on palliative care utilization. However, three factors limit generalizability: (1) lack of a prospective, randomized design; (2) academic study settings with different patient populations and palliative care capacity than most US oncology practices; and (3) referral triggers that require substantial clinician cognitive effort. Our approach of a pragmatic randomized clinical trial is unique. Furthermore, our behavioral intervention, using default referrals based on an automated EHR algorithm, tests a scalable approach to increasing palliative care utilization. Finally, we will use post-intervention semi-structured interviews to refine this approach prior to submitting an R01 application for a multi-institutional randomized clinical trial that includes algorithm-based behavioral strategies to increase palliative care referral in community oncology.

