4.9 ACCRUAL

Patients will accrue to the trial as their clinic or clinician is enrolled. **Included** Tennessee Oncology practices will be randomly assigned to usual care or intervention groups. When enrollment starts, clinicians in the intervention clinics will receive the EHR nudge for palliative care referral for each eligible patient and based on the clinician response (opt-out or default), the research coordinator will call and offer palliative care consultation visit to the patient.

For the semi-structured interviews, participants will be initially recruited via internal practice email (See **Exhibit 6**) from the clinical research coordinator. If we don't receive enough interest, we will then recruit by visiting the clinicians in-person in their clinics. In-person recruitment will be done by site investigator and/or clinical research coordinator at Tennessee Oncology.

Approximately 20 eligible clinician participants from the intervention group will be interviewed (1) in-person, (2) virtually, or (3) via telephone. To ensure an adequate number of perspectives on the trial, we will use purposive sampling to sample clinicians who performed at or above vs. below the median response to the intervention. The clinical research coordinator will email and schedule the interviews through outlook. A confirmation email will be sent to the clinician 24 hours before the interview unless the interview will occur less than 24 hours after scheduling. Two pilot interviews will be conducted and used in analysis (pending major edits are not required).

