- I do not believe this patient's disease or clinical factors warrant palliative care.
- I worry about the patient getting the wrong message with our treatment goals.
- Other – please explain

Sincerely,

[name]

[name]

[name]

EXHIBIT 6

Recruitment Emails for Oncology and Palliative Care Clinicians

Recruitment Email for Oncology Clinicians

Subject: Re: your feedback on upenn palliative care study

Dear Dr. ___ or NP name,

We have completed enrollment for our palliative care clinical trial with University of Pennsylvania and would love your **feedback on being a participant in the intervention group.**

This is a separate qualitative study where you will be interviewed, and your feedback will be incorporated to improve our model for palliative care referrals among patients with advanced lung and non-colorectal GI malignancies.

We are offering a \$100 gift card for your time and participation.

Let me know when a good time for us to meet and conduct the interview for approximately 30 minutes. I can meet with you in person (for middle TN), virtually (zoom or skype), or via telephone.

Thank you for your time and consideration.

Sincerely,
[name]

Recruitment Email for Palliative Care Clinicians

Subject: Re: your feedback on upenn palliative care study

Dear Dr. ___ or NP name,

We have completed enrollment for our palliative care clinical trial with University of Pennsylvania and would love your **feedback on being a palliative care clinician in this study.**

This is a separate qualitative study where you will be interviewed, and your feedback will be incorporated to improve our model for palliative care referrals among patients with advanced lung and non-colorectal GI malignancies.

We are offering a \$100 gift card for your time and participation.

Let me know when a good time for us to meet and conduct the interview for approximately 30 minutes. I can meet with you in person (for middle TN), virtually (zoom or skype), or via telephone.

Thank you for your time and consideration.

Sincerely,
[name]

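### Interviews with intervention-arm oncologists may begin while 3-month primary windows are still open; a stated later start would remove a small possible one-arm bias

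*Combined protocol and SAP*

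**What the plan says.** Section 3.1 gives the only timing rule for the interviews: "After completing initial enrollment, we aim to conduct a qualitative study". The invitation to oncologists in Exhibit 6 rests on the same event: "We have completed enrollment for our palliative care clinical trial with University of Pennsylvania". Section 4.3 gives their length: "We anticipate the semi-structured interviews take approximately three to four months". It expects about 10 oncology clinicians from the intervention group and about 10 palliative care clinicians.

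Among oncologists, only one arm is contacted. Section 4.5 states: "Medical oncology clinicians at Tennessee Oncology that were in control arm will be excluded". Section 3.1 makes barriers to and facilitators of more referrals a subject of these interviews.

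Enrolment and follow-up each last six months (4.3). The primary endpoint is a palliative care visit in the 3 months after a high-risk patient's enrolment (6.4). The secondary outcome is the same kind of visit in non-high-risk patients, with no time window given (3.3, 6.4). No section makes the invitation or the interviews wait until the 3-month windows have closed.

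**The concern.** The outcome depends partly on what clinicians do. A patient enrolled late in accrual can still have, or fail to have, a qualifying visit for up to three months after enrolment closes. If intervention oncologists are invited and questioned about referral in that time, they receive a contact that control oncologists do not. The monthly peer-comparison emails go to both arms (4.6), so that prompt is balanced; the interviews are not.

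The protocol itself accepts that research contact can alter behaviour. Section 8.3 supports the consent waiver partly by saying that asking control-group members for consent might by itself change what they do. Applying that reasoning to an interview is an inference, but a fair one. At stake is a possible addition to the measured effect that is not part of the default referral.

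**Working it through.** The plan gives no figure for this overlap, so there is none to reproduce. The 360 patients in 6.5 serve only as a head count.

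**Inputs.** Enrolment 6 months and interview period 3 to 4 months (4.3); primary window 3 months (6.4); about 10 oncology interviewees (4.3); up to 40 clinicians per arm (4.4), or 20 per arm if the total of 40 in 4.1 is split evenly. **Assumptions, not in the plan:** uniform accrual, equal caseloads, interviews spread evenly over time.

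**1. Open windows.** Let *s* be the months from the last enrolment to the first interview. A patient's window is open at that point if enrolment fell in the last 3 − *s* months of accrual, so the share is (3 − *s*)/6. The share of all primary-window time after that point is [(3 − *s*)²/2]/(6 × 3) = (3 − *s*)²/36.

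| Start after last enrolment | Patients with open window | Of 360 (intervention arm) | Window time still to come |
|---|---|---|---|
| 0 months | 3/6 = 50% | 180 (90) | 9/36 = 25% |
| 1 month | 2/6 = 33% | 120 (60) | 4/36 = 11% |
| 2 months | 1/6 = 17% | 60 (30) | 1/36 = 3% |
| 3 months | 0% | 0 (0) | 0% |

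Faster accrual late in the period raises these shares; faster early accrual lowers them.

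**2. Window time after the treating clinician's own interview.** Take the worst start, *s* = 0, with interviews spread over 3 months. At *t* months after close, a fraction *t*/3 of the interviewees have been interviewed and (3 − *t*)/6 of patients have an open window. For patients of clinicians who are interviewed at some point:

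- ∫₀³ (*t*/3)((3 − *t*)/6) d*t* = (13.5 − 9)/18 = 0.25 months per patient.
- 0.25/3 = 8.3% of their window time.
- With 10 of 40 clinicians: 8.3% × 0.25 = about 2% of intervention-arm window time.
- With 10 of 20 clinicians: 8.3% × 0.50 = about 4%.

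Spreading the interviews over 4 months lowers the integral to 4.5/24 = 0.1875 months, or 6.25% of window time, giving 1.6% and 3.1%. Section 4.9 can be read as about 20 interviewees from the intervention group alone. That would double the results, but 3.1 and 4.3 count palliative care clinicians within the 20.

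**3. Routes to the outcome.** For a flagged patient, the notification goes out, 48 hours pass (Exhibit 5), and the coordinator calls and books (4.6). The oncologist need do nothing. A later contact with the oncologist can therefore act mainly on high-risk patients who were opted out or missed. Opted-out patients include those whose oncologist chose to talk to the patient first, which is one of the Exhibit 5 reasons. In non-high-risk patients there is no default referral, so their visits depend on ordinary referral, which an interview could prompt.

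**The case against.** The strongest reply is that the overlap is permitted, not planned. Section 3.1 says after enrolment and gives no date, and section 4.7 says "we will use post-intervention semi-structured interviews to refine this approach", which could mean a later start. The 50% is thus an upper figure under an immediate start. The tested action is a default carried out by a coordinator, both arms already receive education and peer comparison, and the invitation asks for feedback on a separate study without asking for referrals. All of this stands, and it is why the point is about a missing safeguard. It does not remove the gap, because post-intervention is not defined and the email is tied to enrolment. The email may also reach more clinicians than the 10 or so interviewed, so step 2 does not bound all contact.

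A reader might infer three stronger points that the documents do not support:

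- **Clinicians would be ranked on incomplete outcomes.** Section 4.9 samples those who "performed at or above vs. below the median response to the intervention". The same section uses clinician response for whether the clinician opts out or lets the default run, which is known about 48 hours after each notification. The term is not formally defined, so a visit-based reading is possible but not established. Even then, it would change who is interviewed and not the primary comparison.
- **The blinding is strained.** Section 4.1 says the principal investigator and "primary statistical analyst will be blinded to arm assignment". The same section has the Tennessee Oncology research team draw up the clinician list, and no section gives the ranking to the blinded roles.
- **A quarter of window time is affected.** The 25% is all window time after enrolment closes. It is not time after a clinician has been interviewed.

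**Conclusion.** The gap is real and minor. As written, the plan allows intervention-arm oncologists alone to be invited and interviewed about referral while up to 50% of patients have an open primary window, given an immediate start and uniform accrual. Under the further assumptions of even interviewing and equal caseloads, about 2% to 4% of intervention-arm window time follows the treating clinician's interview.

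The effect of an interview or an email on referral cannot be computed from the documents. Any bias is probably small and likely to favour the intervention. The secondary outcome is more open to it than the primary, because the default referral does not cover non-high-risk patients. The documents do not support a finding that the trial will re-prompt one arm, that the interview sample rests on truncated outcomes, or that blinding is compromised.

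**What to change.** State in 3.1, 4.3 and 4.9 that oncologist invitations and interviews start only after the last enrolled patient's 3-month window has closed, and align the opening line of the Exhibit 6 email. This removes the overlap for the primary endpoint. It does the same for the secondary outcome only if that outcome is also given a 3-month window.

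The cost is modest. Interviews would start at about month 6 + 3 = 9 and end at month 9 + 3 = 12 to 9 + 4 = 13, against a 12-month study, so they may run about one month over. Clinicians would also recall the intervention over a longer interval. Exploratory outcomes are followed for six months and would still overlap. As 6.4 plans only descriptive statistics for them, a longer wait does not seem needed.

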3.2 PRIMARY OUTCOME

Completed palliative care visit within 3 months among high-risk patients with stage III and IV lung and non-colorectal GI malignancies

3.3 SECONDARY OUTCOMES

- Completed palliative care visit among non-high risk patients with stage III and IV lung and non-colorectal GI malignancies.

We will also assess on an exploratory basis the impact on acute care utilization including emergency room visits and hospitalizations within participating hospitals in the state of Tennessee; completed palliative care visits among all patients at Tennessee Oncology, number of opioid prescriptions, aggressive end-of-life care (no hospice referral or enrollment prior to death, hospice enrollment<3 days before death, location of death and/or chemotherapy receipt within 14 days of death); and patient-reported measures such as depression and pain. We will also assess on an exploratory basis the quality of life of patients in the intervention group and control group through the FACIT-PAL 14, and “Heard & Understood” instrument before the palliative care visit, and after the visit at 1-month, 3-month and 6-month intervals (see **Exhibit 4**).

4. STUDY DESIGN

4.1 RANDOMIZATION & RECRUITMENT

This 2-arm randomized trial (six-month enrollment; six-month follow-up) will enroll approximately 400 patients with advanced lung and gastrointestinal malignancies and 40 clinicians to assess response to behavioral nudges to refer to palliative care at up to 17 practices within Tennessee Oncology, a US community oncology network. All practices have access to palliative care and will be randomized to usual care vs. intervention. The outcome is completion of a palliative care visit within 3 months among high-risk patients.

We will randomize practices into two arms using permuted block randomization to balance practice size, baseline palliative care referral rate (see **Exhibit 1**). The Principal Investigator ([name]) and primary statistical analyst will be blinded to arm assignment.

This 2-arm randomized trial (six-month enrollment, six-month follow-up) is taking place at Tennessee Oncology. Tennessee Oncology, one of the nation’s largest, community-based cancer care specialists, is home to one of the leading clinical trial networks in the country.

Eligible clinicians will receive notification about the trial via email and in-person presentations. High-risk patients for the intervention will be identified from weekly runs of the risk score algorithm, in coordination with [name], Tennessee Oncology Care Data Systems Manager.

For the semi-structured interviews, the research team at Tennessee Oncology will create a list of potential clinicians. We will initially contact potential participants via email (see **Exhibit 6**), and if we do not get enough participation, coordinator and site investigator will do in-person recruitment with clinicians. For participants that agree to do the interview, clinical research coordinator will create a research ID for each participant that only key members of research team will have access to. Coordinator will subsequently create a de-identified dashboard to track mode of interview (in-person, virtual, telephone), length of interview, participant characteristics (gender, years in practice, palliative care v oncology, physician v nurse practitioner), and to store audio files, transcripts, and analysis documents. To ensure an adequate number of perspectives on the trial, we will use purposive

sampling to sample clinicians who performed at or above vs. below the median response to the intervention.

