4.4 TARGET POPULATION

Approximately 400 patients with advanced malignancies and up to 80 clinicians to assess response to behavioral nudges to refer to palliative care at up to 17 practices within Tennessee Oncology. The split will be into two arms: approximately 200 intervention, 200 control, and up to 40 clinicians in each arm. Clinicians will be clustered to a single practice for the intervention and analysis in order to avoid contamination of intervention effect into the usual care arm.

Our target population for the semi-structured interviews includes clinicians at Tennessee Oncology that were included either in the intervention group as oncology providers, and palliative care clinicians at Tennessee Oncology that saw patients referred through our intervention.

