6.5 SAMPLE SIZE

Currently, there are approximately 4000 eligible patient-encounters over a six-month period at our study practices. Given prior work showing the algorithm flags 8-10% of eligible patients as high-risk, we anticipate enrolling at least 360 patients. The unit of analysis is the patient. We will use multilevel mixed-effects models, adjusted for relevant covariates, to assess outcomes. Assuming baseline palliative care rate=26.9% (SD=10%), a 10% dropout rate, two-sided alpha=0.05, a sample of 360 patients (180 intervention, 180 control) will provide 80% power to detect a meaningful 15 percentage-point increase in palliative care visits.

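### Section 4.1 says permuted blocks will balance practice size and baseline referral rate but describes no step that would do so; with at most 17 practices this leaves an avoidable risk of chance imbalance.

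*Combined protocol and SAP*

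**What the plan says.** Practices are the randomised units, "at up to 17 practices within Tennessee Oncology, a US community oncology network". Section 4.1 gives the method and its purpose in one sentence: "We will randomize practices into two arms using permuted block randomization to balance practice size, baseline palliative care referral rate". The sentence names no strata, cut-points, block size, matching or constraint. It refers the reader to Exhibit 1, whose text is the table of patient risk factors and contains nothing on allocation. Section 4.9 adds only that allocation of practices is random.

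Section 4.4 expects a near-equal patient split: "The split will be into two arms: approximately 200 intervention, 200 control, and up to 40 clinicians in each arm". Section 6.5 sets the planning values: "Assuming baseline palliative care rate=26.9% (SD=10%), a 10% dropout rate, two-sided alpha=0.05", and states that "a sample of 360 patients (180 intervention, 180 control) will provide 80% power" for a 15-point increase. The patient is the unit of analysis. The planned analysis is a mixed-effects model with covariates that are not named, so neither practice size nor baseline referral rate is committed to it.

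**The concern.** Blocking equalises counts. With 17 practices it yields 8 against 9, whichever practices those are. Unless the blocks are formed within levels of size and referral rate, or the allocation is otherwise restricted, those two factors are left to chance, and 17 units give chance wide scope.

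Baseline referral rate is the more important of the two, because a referral precedes the primary outcome, a completed palliative care visit. If a practice's past rate predicts its rate in the trial and is not adjusted for, a gap between arms at the draw moves the effect estimate by the gap times the strength of that relation. The documents do not give that strength. As an illustration, a 5-point gap moves the estimate by 5 points if the relation is one-to-one and by 2.5 points if it is half that. Practice size matters less. It decides whether the planned equal split of patients is achieved, and it gives large practices more weight in the baseline gap.

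**Working it through.** **Inputs.** From the documents: at most 17 practices (4.1); about 200 patients per arm (4.4); 360 patients, baseline rate 26.9%, SD 10%, 10% dropout, two-sided alpha 0.05, 80% power and a 15-point effect (6.5). Assumptions: the SD of 10% is between practices (6.5 does not say what it describes; 5% is shown as an alternative); the baseline rate in 6.5 stands for the referral rate in 4.1; practice sizes have a coefficient of variation (CV) of 0.4 to 1.0 (the documents give no sizes); size and rate are independent.

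**1. The plan's own figure.** For 26.9% against 41.9%, with mean 34.4%, n per arm = [1.96 × √(2 × 0.344 × 0.656) + 0.84 × √(0.269 × 0.731 + 0.419 × 0.581)]² / 0.15² = 157. Dividing by 0.90 for dropout gives 175 per arm, 350 in total, against the stated 360. With 180 × 0.90 = 162 evaluable per arm, power is 81.4%. The stated 80% is reproduced, treating patients as independent. The documents give no imbalance figure to reproduce.

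**2. Unstratified blocks, practices weighted equally.** SD of the arm difference in mean baseline rate = SD × √(1/8 + 1/9).
- SD 10%: 10 × 0.486 = 4.9 points. P(gap ≥ 5) = P(|Z| ≥ 5/4.86 = 1.03) = 30%. P(gap ≥ 7.5) = 12%. P(gap ≥ 10) = 4%.
- SD 5%: 2.43 points. P(gap ≥ 5) = P(|Z| ≥ 2.06) = 4%.

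**3. Weighted by patients, which is the relevant form because the patient is the unit of analysis.** Results of 100,000 simulated draws with 17 practices and SD 10%, using blocks of four without strata, or blocks of two within four strata (each factor cut at its median):

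| | CV 0.4 | CV 0.65 | CV 1.0 |
|---|---|---|---|
| Unstratified: gap above 5 points | 33% | 37% | 42% |
| Unstratified: gap above 10 points | 5% | 7% | 11% |
| Unstratified: split beyond 60:40 | 7% | 22% | 39% |
| Stratified: gap above 5 points | 16% | 21% | 27% |
| Stratified: gap above 10 points | 1% | 2% | 4% |
| Stratified: split beyond 60:40 | 5% | 16% | 32% |

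Listing all 24,310 allocations of 8 against 9, for CV 0.4 to 0.9, agrees: weighted gaps of 5 points or more in 33-41% and splits beyond 60:40 in about 7-38%. At SD 5% the unstratified weighted figure is 5-10%. With only 12 practices and SD 10%, gaps above 5 points occur in 42-48%.

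**4. Power cost of an uneven split alone** (324 evaluable patients): 81.4% at 50:50, 79.5-80.2% at 60:40 and 77.2-78.3% at 65:35, depending on which arm is larger.

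**5. Effect of constraining the draw** to the best-balanced 10% of allocations at SD 10%, for CV 0.4, 0.65 and 1.0: the SD of the gap falls to 1.3-2.0 points, gaps above 5 points fall to 0.2%, 1% and 7%, and splits beyond 60:40 fall to 0%, 0% and 4%. The score must use the patient-weighted gap. Constraining the unweighted gap still leaves weighted gaps of 5 points or more in about 3-23% of the retained allocations.

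**The case against.** The sentence in 4.1 can be read as shorthand for blocks formed within levels of the two factors. A figure just before the Exhibit 1 table and the trial schema in Exhibit 2 are not shown, so strata might appear there. That stands: the documents show an unspecified method. A reader might infer that the blocks are unstratified and therefore balance nothing but the number of practices; the documents do not establish this. Nor are stratified blocks useless. In the table they cut weighted gaps above 5 points from 33-42% to 16-27%. They do little for the patient split.

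Chance imbalance under randomisation is not bias, and a model with a practice effect carries between-practice variation into the standard error. That also stands. Adjustment could recover much of the lost precision, but section 6.5 does not commit to either factor.

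The size of the risk depends on how the SD of 10% is read, and at 5% it is small. Section 4.4 promises only an approximate split, and a 60:40 split costs little.

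Finally, a full list of allocations needs a fixed set of practices. Section 4.1 gives only an upper limit, and section 4.9 has patients accruing as their clinic or clinician is enrolled. Randomising all practices at once is plausible but not stated, so the fix needs a fallback.

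**Conclusion.** The point holds as a gap between stated purpose and described method, with a cheap and better method available under either reading of section 4.1.

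If the blocks are unstratified and the between-practice SD is 10%, a baseline gap of at least one third of the 15-point target arises in about 30% of draws, or 33-41% when weighted by patients. If that SD is 5%, the figures are about 4% and 5-10%. With median-cut strata, roughly 16-27% remain at SD 10%. Splits beyond 60:40 occur in about 7-38% of unstratified draws for an assumed size CV of 0.4-0.9, and a 60:40 split alone costs only 1-2 points of power.

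A reader might go further and call a large imbalance likely, or the design biased. Neither is supported. Every probability above for a gap of 5 points or more with 17 practices is below one half, gaps above 10 points occur in at most about 11% of draws, and randomisation leaves the estimate unbiased over repeated draws. The issue is the precision and credibility of one draw that cannot be repeated.

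**What to change.** Once the list of participating practices is fixed, replace the sentence in section 4.1 with covariate-constrained randomisation:

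- Score every possible allocation (24,310 for 8 against 9) on the patient-weighted arm difference in baseline referral rate and on the arm difference in expected eligible patients.
- Keep a best-balanced subset, for example 10%.
- Check that no two practices are always or never in the same arm. This matters most when sizes are very unequal; if the check fails, enlarge the subset.
- Have someone outside the study team draw one allocation at random.

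In section 6.5, name baseline referral rate and practice size as covariates in the primary mixed model, and say what the SD of 10% describes. Correct the reference to Exhibit 1.

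If practices cannot all be randomised at once, use permuted blocks within stated strata of the two factors, give the cut-points and block size, and include the strata in the model.

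The cost is a short script before the draw and a paragraph of text, with no added patients or staff. The downside is that the analysis must reflect the constraint.
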